7.0 Background

7.1 Salvage therapy in acute lymphoblastic leukemia (ALL).

Despite an exceptionally high rate of initial CR, many adults with ALL will relapse. Current strategies to induce a second remission translating into long-term survival are lacking. Cytotoxic chemotherapy results in modest CR rates of 30-40% in first salvage and 10-20% in later salvages. Few patients can be bridged to allo-SCT, 5-10% in some studies but as high as 30-40% in the German trials^{1,2}. This bridging to allo-SCT offers a chance of long term remissions and cures (<20-30%). One of the most exciting groups of compounds under investigation in relapsed refractory (R/R) ALL are monoclonal antibodies

targeting CD19 and CD22. Of these antibodies, blinatumomab and inotuzumab ozogamicin are in the most advanced investigational phases (Table 1).

Blinatumomab was granted FDA approval for the treatment of R/R ALL in December 2014. Furthermore, inotuzumab was found to be superior to best available therapy in a randomized trial in patients with R/R ALL and was granted FDA approval for the treatment of R/R B-cell precursor ALL in August 2017.

The randomized trial confirmed the findings of the initial phase II studies. Inotuzumab induces responses in 80% of the patients with a median survival of 7.7 months. The rate of VOD was 10%. The aim of this study is to reduce the rate of VOD without minimizing efficacy.

Table 1. Monoclonal antibodies in relapsed/refractory ALL

Parameter	N (%)			
	Blinatumomab		Inotuzumab	
	Pivotal Study, n=36	Confirmatory Study, n=189	Single dose n=49	Weekly n=40
Overall Response	25 (69)	81 (43)	28 (57)	24 (60)
Salvage Status				
Salvage 1	11 (31)	38 (20)	13 (27)	16 (40)
Salvage 2+	10 (28)	151 (80)	36 (73)	24 (60)
Median survival (months)	9.8	6.1	5.0	9.5

7.2 Inotuzumab ozogamicin

7.2.1 Description

Inotuzumab ozogamicin (INO) consists of a semisynthetic derivative of N-acetyl γ -calicheamicin 1, 2-dimethyl hydrazine dichloride (NAc γ -calicheamicin DMH), a potent DNA-binding cytotoxic antibiotic, attached to a humanized monoclonal IgG4 antibody, G544, directed against the CD22 antigen present on B cells in all patients with mature B-ALL and most patients (>90%) with precursor B-ALL³.

Anti-CD22 monoclonal antibody without conjugated cytotoxic drug has shown to have no anti-tumor activity in preclinical models; instead conjugation with cytotoxic agent provides potent dose-depending cellular damage⁴. This is likely because IgG4 antibodies poorly fix complement, therefore cannot cause apoptosis via complement-mediated and antibody-dependent cytotoxicity⁵.

Calicheamicin is natural product of *Micromonospora echinospora* species, and considered to be intolerantly toxic when not bound to the antibody⁶.

Calicheamicin is linked to the antibody through 4-(4-acetylphenoxy) butanoic acid (acetyl butyrate) which provides stability in physiologic pH and successful

calicheamicin release inside the acidic environment of the lysosomes⁷. INO binds to CD22 receptor on the surface of B-cell, and the CD22 receptor-INO complex is internalized forming an endosome. Subsequently, CD22 receptor-INO complex containing endosome fuses with lysosomes. This is followed by intracellular release of calicheamicin. Calicheamicin binds to the minor groove of DNA in a sequence specific manner, and breaks double-stranded DNA, resulting in cell death.

7.2.2 Pharmacodynamics

Treatment with INO has been shown to provide greater therapeutic benefit, as single agent, compared to CVP or CHOP in B-cell NHL xenografts⁸. INO also showed anti-tumor activity in CVP- and CHOP-refractory tumors; however duration of the INO effect was not as sustained as it was in treatment naïve B-cell NHL xenografts. This observation shows that INO treatment may regress tumor growth in chemotherapy refractory cases, but eventually, some malignant B-cells can escape the anti-tumor activity and re-grow. Gemtuzumab Ozogamicin (GO), another antibody-drug conjugate of NAc γ -calicheamicin DMH, is directed against CD33 antigen, and has been used in treatment acute myeloid leukemia (AML)⁹. However, drug resistance had negative impact on clinical outcome of patients treated with GO¹⁰. It is proposed that the drug resistance was associated with P-glycoprotein (P-gp) expression. P-gp is a membrane glycoprotein that actively pumps cytotoxic agents out of the cells and decreases intracellular concentration the drug¹¹ [Takeshita et al., 2005]. As with GO, INO was also found to be effected with the same resistance mechanism. In a study, INO had no effect on CD22-positive malignant cell lines with P-gp expression compared to parental cells¹¹. In clinical samples, the toxic effect of the INO was inversely related to the amount of P-gp ($p=0.003$). In contrast, the cytotoxicity of INO positively correlated with the amount of CD22 ($p=0.010$).

INO is a CD22-targeted cytotoxic chemotherapy agent without any effector capabilities; in contrast rituximab is a CD20-targeted immunotherapeutic agent with the capability of complement-mediated and antibody-dependent cellular toxicity. Combination of INO and rituximab has been tested in vitro setting, and showed increased cytotoxicity¹². Anti-tumor efficacy of INO and rituximab combination has also been tested in B-cell NHL preclinical models, and demonstrated superior activity with the combination¹³. In a phase 2 clinical trial evaluating the efficacy of INO in relapsed and refractory ALL patients, rituximab was added to the patients with stable or progressive disease after two courses of INO. Addition of rituximab in nine patients with CD20 positive ALL did not provide any additional benefit⁶. Nevertheless, it was a single-arm study with a small number of patients. Efficacy of this combination in ALL patients needs to be evaluated in larger clinical trials.

7.2.3 Pharmacokinetics

Maximum tolerated dose (MTD) was determined as 1.8 mg/m² by a first-in-human clinical trial evaluating the safety of INO in 79 relapsed and refractory NHL patients⁵. Most patients had follicular lymphoma (FL) (44%) and diffuse large B-cell lymphoma (DLBCL) (44%), and 61% of the patients had received \geq 4 prior chemotherapies. Following dose escalation schedules were evaluated: 0.4, 0.8, 1.34, 1.8 and 2.4 mg/m² intravenously (as a 1-hour infusion) once every 3 weeks in MTD lead-in cohort (36 patients). Escalation stop criteria were met as 2 of 6 cohort patients had dose limiting toxicities (one grade 4 neutropenia, one grade 4 thrombocytopenia) at 2.4 mg/m². Thus, 1.8 mg/m² was established as MTD. Reversible thrombocytopenia is one of the main (90%) side effects of INO, and it led to a number of treatment delays. Therefore, declared MTD was evaluated in once every 4 weeks schedule to allow platelet recovery. Dose limiting toxicity was not observed in the six-patient cohort of 1.8 mg/m² once every 4 weeks. As a result, this regimen was used in extended MTD cohort (43 patients). At the end of treatment, objective response rate was 39% among 79 enrolled patients. Administration of INO with a weekly dosing schedule (same total dose of 1.8 mg/m² per cycle) compared to single-dose schedule allowed similar response rates and less toxicity in multiply relapsed B-ALL patients¹⁴. The data showed that inotuzumab ozogamicin disposition was non-linear with number of dose or increasing dose. Non-linearity is seen commonly with other antibodies as well¹⁵. Non-linear pharmacokinetics of monoclonal antibodies is due to target-mediated drug disposition, in which elimination and distribution are affected by the antibody and target cell interaction¹⁶. Anti-CD22 antibody and total calicheamicin followed similar elimination trend, and the free calicheamicin concentration remained less than 50 pg/mL overtime, suggesting that the acetyl butyrate linker is noticeably stable in plasma⁵.

7.3 Inotuzumab in R/R ALL

7.3.1 Single agent inotuzumab ozogamicin

Initial studies in patients with lymphoma established an MTD of 1.8 mg/m² IV given every 3 to 4 weeks, with reversible thrombocytopenia emerging as a frequent adverse effect.⁵ This led to a single institution phase II study in patients with relapsed-refractory ALL⁶. The starting dose was 1.3 mg/m² IV every 3 to 4 weeks for the first three patients; later patients received 1.8 mg/m².

Acetaminophen, diphenhydramine, and hydrocortisone were administered to prevent infusion reactions. Forty-nine patients were treated, 73% of whom received inotuzumab for Salvage 2 or later. The ORR was 57%, and the median survival was 5.1 months (Table 2). Nearly half of the patients treated with inotuzumab were able to proceed to ASCT (n = 22), including four patients who were receiving their second ASCT. Survival was similar whether patients underwent subsequent ASCT or not.

To optimize the benefit:risk of inotuzumab, a weekly dosing regimen was evaluated based on preclinical studies indicating that toxicity might be minimized while maintaining efficacy (Table 2).¹⁴ Inotuzumab was given at 0.8 mg/m² on Day 1, and 0.5 mg/m² on Days 8 and 15, every 3-4 weeks. This is the same cumulative dose per course compared with single infusion inotuzumab every three to four weeks. With the weekly regimen, ORR was similar to the single-dose schedule (59% versus 57%). The median survival was 9.5 months. The weekly regimen was less toxic. Additionally, 37 patients with relapsed/refractory ALL received weekly inotuzumab in a multicenter phase I/II study¹⁷. Seventeen (46%) patients were in Salvage 1, 9 (24%) in Salvage 2, and 11 (30%) in Salvage 3 or later. The CR and CR without count recovery rates were 79% (19/24) and 46% (6/13) in the dose expansion and dose escalation cohorts, respectively. Eighteen of the nineteen patients in the dose escalation cohort and four of the six in the dose expansion cohort achieved MRD negativity. These encouraging results led to an international study comparing weekly inotuzumab to standard ALL chemotherapy (FLAG at MD Anderson) in ALL salvage 1-2. The objective response rates were 81% and 33%, respectively. Among responders, the MRD-negativity rates were 78% and 28%, respectively. The median response duration was 4.6 versus 3.1 months (p=0.017), respectively.

Table 2. Activity of inotuzumab ozogamicin in patients with relapsed/refractory ALL

Parameter	N (%)		
	Single-Dose, n=49	Weekly, n=40	Overall, n=89
Response			
CR	9 (18)	8 (20)	17 (19)
CRp	16 (33)	13 (33)	29 (33)
CRi, bone marrow CR	3 (6)	3 (8)	6 (7)
PR	0	0	0
Resistant	18 (37)	14 (35)	32 (36)
Death < 4 weeks	3 (6)	2 (5)	5 (6)
Salvage			
Salvage 1	13 (27)	16 (40)	29 (33)
Salvage 2+	36 (73)	24 (60)	60 (67)
Median survival (months)	5.0	9.5	6.2

7.3.2 Combination of inotuzumab ozogamicin with chemotherapy

Given the promising results in the salvage studies, inotuzumab was evaluated in combination with chemotherapy. A group of patients with ALL who may particularly benefit from a more targeted regimen is elderly patients (age greater than 60 years). This group is predisposed to severe toxicity from conventional chemotherapy, which is associated with high mortality rate (30-35%) during consolidation-maintenance in CR. Thirty-four older patients (median age of 69 years; range, 60 to 79) with newly diagnosed ALL were treated in a phase II study combining inotuzumab and low-intensity hyperCVAD therapy.¹⁸ The

regimen eliminated doxorubicin in induction, used cyclophosphamide and steroids at 50% of the dose of previous regimens, and reduced methotrexate to 250 mg/m² on Day 1 and cytarabine to 0.5 mg/m² x4 (Days 2 and 3) of even courses. Inotuzumab 1.3-1.8 mg/m² was given once with each of the first 4 courses. The ORR was 97% (CR 83%). All patients with cytogenetic abnormalities achieved complete cytogenetic response. All patients achieving response also had a negative MRD status, 75% of them after one cycle. The 2-year progression-free and overall survival rates were 87% and 70%, respectively. The 2-year survival rate was superior to previous results obtained with HCVAD +/- rituximab in similar patient populations (2-year survival rates 70% and 38%, respectively).

This combination was also assessed as a salvage therapy in 48 patients. The ORR was 74% (CR 52%) The 12-month progression-free and overall survival rates were 88% and 81%, respectively¹⁹.

7.4 Inotuzumab ozogamicin toxicity profile

Transient fever and hypotension were the 2 most frequent non-hematologic adverse events, and typically occurred shortly after the inotuzumab infusion. Liver function abnormalities were also observed, but tended to be reversible. Serious toxicity in the transplant group included the development of veno-occlusive disease (VOD) in five patients (23%). Four of the 5 patients had received multiple alkylating agents in the transplant preparative regimen, including clofarabine which may have predisposed them to VOD. Two of the 4 patients undergoing second ASCT developed VOD, suggesting this group of patients to be also at higher risk for VOD. In elderly ALL and in combination with low intensity chemotherapy, 4 patients (11%) developed a VOD, one of them post allogeneic stem cell transplantation. All but one patient had mild VOD that resolved subsequently. Only one patient developed a Grade 5 VOD after 2 cycles, was switched to miniHCV and ofatumumab, received 2 more additional courses, developed anasarca and multiple organ failure and expired thereafter. The safety profile of inotuzumab ozogamicin vs standard of care (SOC) was consistent with the initial studies. For inotuzumab vs SOC, Gr≥3 hepatobiliary AEs occurred in 9% vs 3% patients; any grade VOD occurred in 15 (14%) vs 1 (0.9%) patient (Gr≥3, 13 vs 1 patients). More patients proceeded to ASCT with inotuzumab (n=48) vs SOC (n=20); in the inotuzumab arm, 5 VOD cases (2 in patients with prior ASCT) occurred during treatment and 10 after subsequent SCT (2 fatal).

8.0 Background Drug Information

8.1 Inotuzumab

8.1.1 Formulation and packaging

Inotuzumab ozogamicin is a white to off-white powder or cake, lyophilized, unpreserved 1- mg or 4-mg protein equivalent powder for intravenous injection in an amber vial.

8.1.2 Preparation and dispensing

Specific preparation and dispensing instructions for inotuzumab ozogamicin are provided in the Dosage and Administration Instructions. Once inotuzumab ozogamicin has been prepared following the Dosage and Administration Instructions, the site pharmacist will label the study medication in accordance with local requirements. Only qualified personnel who are familiar with procedures that minimize undue exposure to them and to the environment should undertake the preparation, handling, and safe disposal of chemotherapeutic agents.

8.1.3 Administration

All patients must be weighed within 7 days prior to every cycle day 1 dosing to ensure they did not experience either a weight loss or gain >10% from the prior weight used to calculate the amount of inotuzumab ozogamicin required for dose preparation. Decision to recalculate the dose of inotuzumab ozogamicin based on the weight obtained at each cycle can be in accordance with institutional practice; however, if the patient experienced either a weight loss or gain >10%, the required amount of inotuzumab ozogamicin needed for study drug preparation and administration must be recalculated using this most recent weight/BSA obtained. If the dose administered is 10% greater or lower than the one prescribed, it will be reported as a dosing medication error.

Inotuzumab ozogamicin is administered intravenously. Subjects will receive a dose of 1.8 mg/m² over the first cycle (0.8 mg/m² on D1, 0.5 mg/m² on D8 and D15 [+/- 3 days]) of 21 to 28 days cycle. The remaining 5 cycles (total of 6 overall) will consist of 0.9 mg/m² administered in 2 divided weekly doses of inotuzumab ozogamicin (0.6 mg/m² on Day 1 [+/- 3 days], 0.3 mg/m² on day 8 [+/- 3 days]) over a 21- to 28-day cycle.

Pretreatment: Prior to inotuzumab ozogamicin treatment, subjects should receive pretreatment medications to reduce the incidence and severity of an anticipated infusion syndrome characterized by fever and chills, and less commonly hypotension. Pretreatment prior to inotuzumab ozogamicin includes corticosteroid, antipyretic, and antihistamine. Premedication before inotuzumab ozogamicin may also include antiemetics. Antiemetics with the least potential of side effects are recommended. Subjects should be pretreated with methylprednisolone (or other corticosteroid), acetaminophen/paracetamol and diphenhydramine (or other antihistamine) approximately 0.5 to 2 hours before each inotuzumab ozogamicin administration. In cases of infusion reactions, discontinue infusion and institute appropriate medical treatment as needed (eg, glucocorticosteroids, epinephrine, bronchodilators, or oxygen). Depending on the

severity of the infusion reaction and interventions required, the investigator could consider restarting the infusion at a reduced rate.

Reconstituted inotuzumab ozogamicin will be administered over approximately 1 hour by intravenous infusion unless the subject requires temporary interruption of the administration.

Vital Signs during inotuzumab administration:

- Cycle 1 Day 1 (first inotuzumab infusion): Prior to inotuzumab, approximately 30 minutes into infusion, just prior to end of infusion, approximately 1 hour and approximately 2 hours after end of infusion.
- All Subsequent infusions: Prior to inotuzumab and at end of infusion (+/- 15 min).

8.1.4 Recommended dose modifications

In the event of significant toxicity, dosing may be delayed as described below. In the event of multiple toxicities, dose modification should be based on the worst toxicity observed. Patients are to be instructed to notify Investigators at the first occurrence of any adverse symptom.

Dose modifications may occur as follows:

1. Within a cycle: dose interruption until adequate recovery (Grade ≤ 1) or omission of a dose during a given treatment cycle.
2. Between cycles: next cycle administration may be postponed due to toxicity in the previous cycle.
3. In the next cycle (Cycle 3 and beyond): dose reduction based on worst toxicity or to 0.6 mg/m²/cycle if hematologic remission is achieved in the previous cycle.

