5.0 Evaluation During Study

Procedure	Comments	Schedule
Hematology	CBC with differential and platelet count	Weekly during cycles 1 to 6
Biochemistry	at least creatinine, total bilirubin, SGPT or SGOT	Cycle 1, prior to study drug infusion Cycle 2-6, prior to each study drug infusion and/or at the discretion of the treating physician.
Physical Examination	Focused physical examination	Prior to each treatment cycle
Bone marrow	Aspirate and/or biopsy (MRD) by flow multicolor cytometry and by polymerase chain reaction (PCR).	On day 14, 21 +/- 3 days of the first cycle, then every 2-3 cycles.

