6.0 Criteria for Response

Complete remission (CR):

Normalization of the peripheral blood and bone marrow with 5% or less blasts with a granulocyte count of $1 \times 10^9/L$ or above and a platelet count of $100 \times 10^9/L$ or above and absence of extramedullary disease.

Complete remission without platelet recovery (CRp):

As above except platelets $< 100 \times 10^9/L$

Complete remission with incomplete count recovery (CRI):

CR without recovery of neutrophils or platelet counts

Partial response (PR):

As above, except for the presence of 6-25% marrow blasts.

MRD negativity:

MRD levels will be continuously assessed during induction and consolidation therapy by 6-color multiparameter flow. MRD negativity will be defined by a value of no more than 10^{-4} and confirmed on a second bone marrow aspiration/biopsy performed after a subsequent cycle.

No response (NR):

Patients will be considered non-responders if no response is achieved after 2 cycles.

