8.1.5 Dose delays

If patients do not meet the criteria below on the day of the scheduled treatment, the administration of the dose will be delayed.

1. No evidence of progressive disease or relapse prior to the start of each cycle; however, treatment may continue, at the judgment of the investigator, in patients with only extramedullary CNS and/or testis relapse.
2. Prior to the start of each cycle, decrease in blast percentage or stable disease (ie, not more than a 50% increase in blast percentage) based on the most recent bone marrow evaluation.
3. Recovery to grade 1 or baseline non-hematologic clinically significant test article-related toxicity (including liver function test abnormalities, not including alopecia).

4. Serum bilirubin $\leq 1.5 \times$ ULN, and AST or ALT $\leq 2.5 \times$ ULN (or if elevated due to tumor, bilirubin $\leq 2 \times$ ULN). Isolated AST or alkaline phosphatase elevations need not result in dose delays if not related to hepatobiliary organs (eg, alkaline phosphatase elevations due to bone involvement). Inotuzumab ozogamicin dosing should be permanently discontinued for any patients with possible, probable or confirmed VOD or other severe liver toxicity.
5. Any serum creatinine level associated with a measured or calculated creatinine clearance ≥ 15 mL/min using the method standard for the institution.
6. Prior to the start of each cycle, for subjects with pre-treatment ANC $\geq 1 \times 10^9/L$: ANC $\geq 1 \times 10^9/L$.
7. Prior to the start of each cycle, for subjects with pre-treatment platelets $\geq 50 \times 10^9/L$: platelets $\geq 50 \times 10^9/L$.
8. Subjects with pre-treatment ANC $< 1 \times 10^9/L$ and/or platelets $< 50 \times 10^9/L$: ANC and platelets must recover to baseline values obtained for the prior cycle, or ANC $\geq 1 \times 10^9/L$ and platelets $\geq 50 \times 10^9/L$, or the most recent bone marrow must demonstrate stable or improved disease, and the ANC and platelets are believed to be low due to disease.

There are no ANC or platelet count requirements for Cycle 1 day 1, as dosing criteria are relative to pre-treatment values. While doses given within a treatment cycle (ie, day 8) need not be delayed due to neutropenia or thrombocytopenia, dose delays within a cycle are recommended for non-hematologic toxicity.

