8.3 Recommendations to reduce the risk of VOD for patients proceeding to ASCT

- For patients planning to receive an allogeneic ASCT, it is recommended that treatment with inotuzumab ozogamicin be limited to 2 cycles of induction or the fewest number of cycles required to achieve a CR/CRi/CRp (if CR/CRi/CRp not achieved after 2 cycles).
- The risk of relapse must be balanced against the potential risk of toxicity associated with beginning ASCT soon after the last dose of inotuzumab ozogamicin; however, approximately 5-6 weeks between inotuzumab and ASCT may be reasonable for most patients.
- Healthcare providers should use their clinical judgment to determine the most appropriate course of therapy for prophylactic treatment before the start of conditioning therapy according to standard of care (eg, prophylactic ursodeoxycholic acid at 12-15 mg/kg/day, beginning 2 weeks before the start of conditioning therapy).
- Use the least hepatotoxic conditioning regimen and, specifically, avoid using regimens that contain 2 alkylating agents and or that combine an alkylating agent with higher dose TBI (defined as >12 Gy).
- If using a busulfan-containing conditioning regimen, please consider using pharmacokinetically-dosed busulfan.
- When possible, avoid the concomitant use of hepatotoxic drugs peri-transplant.
- If significant liver toxicity occurs, consult a gastroenterology and/or hepatology service.
- When evaluating liver toxicity, inform the radiologist of the potential for hepatic vascular disease. When VOD is in the differential diagnosis, a right upper quadrant ultrasound with colorflow doppler (including resistive indices to hepatic artery flow and evaluation of hepatic venous outflow) should be performed. In addition, the radiology report should describe the degree of gall bladder wall thickening in millimeters and the volume of ascites should be estimated as closely as possible (i.e., small and localized, moderate and generalized, or large and generalized).
- Defibrotide may be used in the setting of severe VOD
- If a patient will proceed to ASCT under the care of different physicians, these recommendation should be reviewed with the new treating physicians.

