10.0 Criteria for Removal from the Study

Criteria for removal from study include, but are not restricted to, the following:

10.1 No response after 2 cycles or progressive disease, unless considered by the treating physician and after discussion with the PI to be in the best interest of the patient. In this situation, if the treatment is well tolerated, patient can receive up to a maximum of 4 cycles.

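### Can a remission first reached in cycle 2 drop out of the primary endpoint because no marrow is fixed in that cycle?

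*Combined protocol and SAP*

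**What the plan says.** All references are to the combined protocol and SAP.

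- **Primary endpoint (11.0).** CR, CRp or CRi at any time during treatment. The Simon rule needs at least 7 of the first 18 patients, then at least 21 of 48.
- **Definition of remission (6.0).** CR requires "Normalization of the peripheral blood and bone marrow with 5% or less blasts", and CRp and CRi are defined from CR. The weekly blood count cannot establish any of them.
- **Marrow schedule (5.0).** "On day 14, 21 +/- 3 days of the first cycle, then every 2-3 cycles". Section 3.3 gives the same two days without naming a cycle, but uses the result to time the start of cycle 2. Neither 5.0 nor 5.1 lists an end-of-treatment marrow.
- **Two-cycle rule.** Section 6.0: "Patients will be considered non-responders if no response is achieved after 2 cycles". Section 10.1 lists as a reason for removal "No response after 2 cycles or progressive disease, unless considered by the treating physician", and after discussion with the PI a "patient can receive up to a maximum of 4 cycles".
- **Optional dose step (8.1.4, item 3).** From cycle 3, a reduction for toxicity "or to 0.6 mg/m²/cycle if hematologic remission is achieved in the previous cycle". The list is introduced as modifications that may occur.
- **Start-of-cycle criterion (8.1.5, item 2).** Judged "based on the most recent bone marrow evaluation".

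**The concern.** Several rules look back at cycle 2, and the assessment table does not guarantee a marrow there. A patient with more than 5% blasts after cycle 1 could follow 5.0 to the letter and reach the two-cycle decision with only the cycle 1 marrows on file. If cycle 2 had in fact produced a remission, the patient could be recorded as a non-responder, leave the study, and never be counted. The same could happen if the patient went to transplant, relapsed or died before the next marrow.

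The stake is the primary endpoint. Missed remissions lower the count at both Simon decisions, so power falls and a stage 1 stop becomes more likely. For the dose step in 8.1.4, the table does not guarantee a marrow in each previous cycle to which the step refers.

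**Working it through.** **1. Where 5.0 can place the marrows.** Four regular readings:

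| Reading | Marrow cycles | Cycle 2 included? | Cycles 3–6 with a marrow in the previous cycle |
|---|---|---|---|
| Every 2, counted from cycle 1 | 1, 3, 5 | no | 4 and 6 |
| Every 3, counted from cycle 1 | 1, 4 | no | 5 |
| Every 2, by cycle number | 1, 2, 4, 6 | yes | 3 and 5 |
| Every 3, by cycle number | 1, 3, 6 | no | 4 |

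The list is not exhaustive, because a range of two to three cycles also allows mixed intervals such as 1, 2, 5. A cycle 2 marrow is therefore permitted but not required.

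**2. What the two-cycle rule needs.** It asks whether a response has been reached after two cycles, and 6.0 defines response by marrow blasts. A marrow from cycle 1 describes the patient after one cycle and cannot answer that question. Where the protocol is content with an older marrow it says so, as in 8.1.5 item 2; 6.0 and 10.1 do not. Nothing directs removal as a non-responder on a cycle 1 marrow alone. Section 8.3 likewise advises transplant candidates to stop at the fewest cycles needed for remission, which presupposes that remission status is known.

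**3. Reproducing the design.** Inputs from 11.0: n1 = 18, continue if at least 7; N = 48, success if at least 21; rates 0.35 and 0.50.

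- P(success | p) = Σ over x = 7…18 of P(Bin(18, p) = x) × P(Bin(30, p) ≥ 21 − x)
- P(stage 1 stop | p) = P(Bin(18, p) ≤ 6)
- E[N] = 18 + 30 × (1 − P(stage 1 stop))

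At p = 0.35: success 0.1127, stop 0.5491, E[N] = 18 + 30 × 0.4509 = 31.53. The plan states 0.113, 0.549 and 31.5. At p = 0.50: success 0.7853 (plan: 78.3%), stop 0.1189, E[N] = 18 + 30 × 0.8811 = 44.43. The design arithmetic is sound.

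**4. What a loss would do.** Let f be the share of true remissions never documented. The counted rate is then p × (1 − f). The documents give no time to remission, so f is purely an assumption. Expected remissions at a true 50% rate are 0.50 × 44.43 = 22.2.

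| f (assumed) | Counted rate at true 50% | Power | Stage 1 stop | Remissions missed (f × 22.2) | P(success) at true 35% |
|---|---|---|---|---|---|
| 0 | 0.500 | 78.5% | 11.9% | 0 | 0.113 |
| 2% | 0.490 | 74.7% | 13.7% | 0.4 | 0.095 |
| 5% | 0.475 | 68.3% | 16.7% | 1.1 | 0.071 |
| 10% | 0.450 | 56.1% | 22.6% | 2.2 | 0.042 |

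The last column shows the direction: false-positive risk only falls.

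**5. How f arises.** It is the product of three shares: remissions that first appear in cycle 2; of those, the ones with no marrow in that cycle; and of those, the ones where the patient leaves, is transplanted, relapses or dies before the next marrow. Each must be at least as large as f. If investigators take a marrow before declaring failure, the removal route closes.

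**6. Two reasons the table may overstate the effect.** Section 11.0 also says that, with fewer than 7 responders among 18, accrual is suspended until 7 are reached. A patient continued under 10.1 could still supply one, whereas the stop column treats 6 or fewer as final. And 11.0 does not say that 35% and 50% are true rates rather than rates of documented remission; if they are the latter, deducting f counts the loss twice.

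**The case for a change.** The strongest case for acting is that the gap is real and cheap to close. CR, CRp and CRi cannot be declared without a marrow; 6.0 and 10.1 turn on status after two cycles; and a site could comply fully with 5.0 without obtaining one in cycle 2. The second marrow mentioned in 6.0 confirms MRD negativity already seen, so it does not help a patient not yet in remission. Someone removed without a marrow cannot later become a documented responder, whatever the suspension clause says. Small losses also matter: about two missed remissions in 22 would cost roughly 22 points of power (78.5 − 56.1 = 22.4).

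What stands is that 5.0 does not name a cycle 2 marrow, and that power is sensitive to missed remissions if they occur. What does not stand is the step from a permitted but unnamed assessment to an expected loss. That needs investigators to declare a marrow-defined failure without a current marrow, or patients to be transplanted, relapse or die before the next one, often enough to matter. The documents support no value of f.

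The dose step in 8.1.4 adds nothing on this point. It is permissive, it concerns patients already known to be in remission, and whether it is used does not alter who counts as a responder.

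**Conclusion.** No change to the plan. This is an under-specified assessment schedule, not a contradiction: 5.0 leaves room for the marrow that 6.0 and 10.1 presuppose, and an investigator can be expected to obtain it before calling a patient a non-responder.

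The candidate remedies gain little. Requiring a further marrow adds an invasive procedure for patients who would not otherwise have one. Letting the rules rest on an earlier marrow would not recover a missed remission. A sentence on counting patients without a cycle 2 marrow would repeat what 11.0 implies, since only patients who meet the endpoint count among the 18 and the 48, and the rest are failures.

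The effect is zero if remissions first reached in cycle 2 are documented then or at a later marrow. Otherwise it is conservative: power at a true 50% rate would be 74.7% to 56.1% for assumed losses of 2% to 10%, with type I error at or below 0.113. This rests on the expectation that investigators judge response on a current marrow. No view is taken on the dose or removal rules themselves.
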